5.2 Secondary Safety Endpoints

The secondary safety endpoints are the following:

- Serious or severe hypersensitivity reaction starting on or after the treatment with iron isomaltoside (i.e. treatment-emergent). The hypersensitivity terms are defined as standardised Medical Dictionary for Regulatory Activities query (SMQ) terms (including four additional terms) in Appendix A.
- Composite cardiovascular adverse events (AEs) starting on or after the treatment with iron isomaltoside (i.e. treatment-emergent). The adjudicated composite AEs includes the following:
 - Death due to any cause
 - Non-fatal myocardial infarction
 - Non-fatal stroke
 - Unstable angina requiring hospitalization
 - Congestive heart failure requiring hospitalization or medical intervention
 - Arrhythmias
 - Hypertension
 - Hypotension

The AEs will be adjudicated by an independent clinical events classification committee (described in a separate adjudication charter). The specified definition of adjudicated endpoints is given in Appendix B.

- Time to first composite cardiovascular safety AE
- Serum (*s*-) phosphate < 2 mg/dL at any time from baseline to month 6

In addition, physical examinations and measurements of vital signs, height, weight, electrocardiogram (ECG), and safety laboratory parameters will be measured as part of standard safety assessments.

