12 ADVERSE EVENTS

12.1 Definition of Adverse Events

An AE is defined in the ICH-GCP guideline as “any untoward medical occurrence in a subject or clinical investigation subject administered a pharmaceutical product and that does not necessarily have a causal relationship with this treatment” (ICH E6:1.2). An AE can therefore be any unfavourable and unintended sign, symptom, or disease temporally associated with the use of a medicinal product, whether or not considered related to the medicinal product. A clinically significant abnormal laboratory finding is also regarded as an AE if the effect is unfavourable for the subject. It is the responsibility of the Investigator to review the laboratory test results and determine whether an abnormal laboratory value is clinically significant. In general, a clinically significant laboratory value which suggests disease progression and/or requires active management is considered as an AE. Clinical significant efficacy laboratory parameters (including related parameters) are not to be recorded as AEs unless these are considered lack of efficacy or overdose.

Clinical significant findings in physical examinations and ECGs are to be recorded as medical history if they are observed at baseline. Otherwise they should be recorded as AEs.

Worsening of a pre-existing medical condition (e.g. cancer or diabetes) must also be recorded as an AE (e.g. if there is an increase in severity, frequency, duration of the condition or worsening of outcome). Pre-planned procedures and pre-existing medical conditions (planned or present at the time of signing the ICF) that have not worsened are not considered AEs. These are recorded on the medical history pages of the electronic case report form (eCRF).

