5. Congestive heart failure requiring hospitalization or medical intervention will meet the following criteria:

1. Requires hospitalization defined as an admission to an inpatient unit or a visit to an emergency department that results in at least a 12-hour stay (or a date change if the time of admission/discharge is not available)

AND

2. Clinical manifestation of congestive heart failure including at least one of the following: new or worsening dyspnoea, orthopnoea, paroxysmal nocturnal dyspnoea, oedema, pulmonary basilar crackles, jugular venous distension, or radiological evidence of worsening heart failure

AND

3. Additional/increased therapy
 - a. Intravenous treatment with diuretic, inotrope, or vasodilator therapyOR
 - b. Mechanical or surgical intervention (mechanical circulatory support, heart transplantation, or ventricular pacing to improve cardiac function) or the use of ultrafiltration, hemofiltration, or dialysis that is specifically directed at treatment of heart failure

6. Arrhythmia will be defined as any symptomatic deviation from normal sinus rhythm experienced by the subject that results in an evaluation by a health care provider. The evaluation may include a physical exam during an outpatient visit, an ECG, or a hospital admission. Arrhythmias may include any conduction abnormality, atrioventricular heart block, prolongation of QTc interval, supraventricular/nodal arrhythmia, vasovagal episode, ventricular arrhythmia, or other cardiovascular arrhythmia.

7. Hypertension

- During the observation period immediately following trial drug administration, hypertension will be defined as an increase in systolic blood pressure > 20 mm Hg that results in a value > 180 mm Hg or an increase in diastolic blood pressure > 15 mm Hg that results in a value > 105 mm Hg
- Following the release of a subject from the trial visit during which they are receiving medication, hypertension will be defined as requiring an unscheduled outpatient health care visit, a hospital admission, or a change in medical therapy (e.g. administration of antihypertensives) in conjunction with the objective criteria, a rise in blood pressure (an increase in systolic blood pressure > 20 mm Hg that results in a value > 180 mm Hg or an increase in diastolic blood pressure > 15 mm Hg that results in a value > 105 mm Hg)

Trial ID: P-Monofer-IDA/CKD-EXT-01

Protocol Version: 2.0 (amendment 1)

Date of Document : 14 June 2017

8. Hypotension

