- During the observation period immediately following trial drug administration, hypotension will be defined as a decrease in systolic blood pressure > 20 mm Hg that results in a value < 90 mm Hg or a decrease in diastolic blood pressure > 15 mm Hg that results in a value < 50 mm Hg.
- Following the release of a subject from the trial visit during which they are receiving medication, hypotension will be defined as requiring an unscheduled outpatient health care visit, a hospital admission, or a change in medical therapy (e.g. fluid/volume repletion, holding of antihypertensives) in conjunction with the objective criteria, a decrement in blood pressure (a decrease in systolic blood pressure > 20 mm Hg that results in a value < 90 mm Hg or a decrease in diastolic blood pressure > 15 mm Hg that results in a value < 50 mm Hg).

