7.3.3 Other Safety Assessments

ECG and Physical Examination

Standard 12 lead ECG and Physical examination is assessed at baseline and at week 26. At baseline, two ECGs will be recorded; one before administration of the trial drug and one approximately 30 minutes after start of the dosing. ECG and each body system of the physical examination will be evaluated as normal or abnormal, and if abnormal clinical significant or not.

The 3 categories of ECG will be presented overall by shift tables from baseline (before treatment) till after dosing and week 26. The shift tables will be repeated by lead in trial. Similar shift tables from baseline till week 26 will be made for physical examination worst case. All data will be listed.

Vital Signs

Vital signs (heart rate, systolic and diastolic blood pressure) will be measured at baseline, weeks 2, 13, and 26. At baseline, vital signs will be measured at the following time points:

- Approximately 0-10 minutes before infusion, during infusion, 5-15 minutes, and 20-40 minutes after the infusion has ended

Vital signs will be summarized by treatment, week and time point, including change from pre- infusion at the treatment visit. The summary tables will be repeated by lead in trial. Vital signs will be listed by subject.

Height and Weight

Height is measured at baseline. Weight is measured at baseline and at the final visit.

Height will be summarised by treatment for the pooled data overall, and by lead in trial.

Weight will be presented in summary tables by treatment and week including change from baseline. This will be made for the pooled data overall, and by lead in trial. All data will be listed by subject.

Laboratory Safety Data

Safety laboratory parameters (haematology and biochemistry) are measured at baseline and at week 2, 13, and 26.

Laboratory safety data will be summarised using descriptive statistics, including means, medians, SDs, and minimum and maximum by week, overall and by lead-in-trial. Furthermore, changes from baseline will summarised. In addition, laboratory safety data will be plotted using boxplots by week.

Values outside normal ranges will be flagged. All safety laboratory data will be listed by lead-in-trial and subject including eligibility laboratory assessments. Clinical significant laboratory will be listed including the corresponding AE.

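### Post-infusion hypertension and hypotension are defined by blood-pressure readings alone, but no stated rule brings a qualifying reading into the composite cardiovascular endpoint, which counts reported AEs

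*SAP*

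**What the plan says.** Protocol Appendix B gives hypertension and hypotension two definitions each, depending on timing.

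- While the subject is under observation after dosing, the criteria are numerical only. Item 7 begins "During the observation period immediately following trial drug administration, hypertension will be defined as an increase in systolic blood pressure > 20 mm Hg" and adds the value that must be reached. Item 8 is built the same way: "hypotension will be defined as a decrease in systolic blood pressure > 20 mm Hg that results in a value < 90 mm Hg". Both have a diastolic alternative. Neither asks for symptoms, treatment or a report.
- After the subject leaves the visit, the reading alone is no longer enough: "hypotension will be defined as requiring an unscheduled outpatient health care visit, a hospital admission, or a change in medical therapy", together with the same limits.

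The endpoint itself is made of adverse events. Protocol 5.2 lists composite cardiovascular AEs and continues: "The AEs will be adjudicated by an independent clinical events classification committee", with the procedure left to a separate charter. SAP 7.3.1 tabulates the composite among the TEAEs, runs time to first event to the date of the adjudicated AE, and censors subjects who report none at their last attended visit.

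Blood pressure is measured before the infusion, during it, and at 5-15 and 20-40 minutes after it ends (Protocol 7.8; SAP 7.3.3). For these readings the SAP plans the following: "Vital signs will be summarized by treatment, week and time point", with change from the pre-infusion value, and a listing by subject.

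Protocol 12.1 explains when laboratory, physical-examination and ECG findings become AEs. For the last two it says: "Clinical significant findings in physical examinations and ECGs are to be recorded as medical history if they are observed at baseline", and otherwise as AEs. Vital signs are not named.

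**The concern.** The protocol supplies an objective definition for the post-dosing events and collects the readings needed to apply it to every dosed subject. The analysis plan does not apply it. A subject without symptoms whose pressure meets the Appendix B limits, and whose investigator does not record an AE, has met the protocol's definition of the component but has no stated path into the composite.

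The described process works in one direction. The committee can reject a reported AE that fails Appendix B, but no described step adds a qualifying reading that nobody reported. Incomplete reporting can therefore only lower the count. It would do so just after the trial's single infusion, in an open-label, one-armed trial whose primary objective is safety.

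**Working it through.** The documents state no figure for this point, so there is none to reproduce. The check is a comparison of texts, followed by an illustration of scale.

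**Tracing a qualifying reading**

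1. Does it meet the component definition? Yes, on numbers alone, if it falls in the post-dosing observation period (Appendix B, items 7 and 8).
2. Must the site record it as an AE? No specific rule says so. Protocol 12.1 has explicit rules for laboratory, physical-examination and ECG findings only. The general AE definition there is wide enough to include it, so recording it is open to the investigator's judgement.
3. Is it sent to the committee if it is not an AE? Protocol 5.2 sends AEs. Anything further would have to be in the charter.
4. Does the SAP detect it? No. Section 7.3.3 applies no Appendix B limit and sets no flag. A table of means, quartiles, minimum and maximum cannot show whether one subject met both the change and the value criterion. The listing can, but only if someone reads it for that purpose.
5. Does the SAP use measured values for other endpoints? Yes. Phosphate below 2 mg/dL, also a secondary safety endpoint, is identified directly from laboratory values (SAP 7.3.2).

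**Illustration of scale**

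Inputs: N = 100, the recruitment target (SAP 3.3.1). Two quantities are assumptions, because the documents give neither: p, the share of subjects with a qualifying post-infusion reading, taken as 1% to 10%; and c, the fraction of those recorded as AEs, taken as 0 to 100%.

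Expected number counted = N × p × c. Probability that none is counted = (1 − p × c)^N.

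At p = 5%, 100 × 0.05 = 5 subjects are expected to qualify, and the probability of at least one is 1 − 0.95^100 = 0.994.

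| Fraction reported, c | Expected counted | P(none counted) |
|---|---|---|
| 0% | 0 | 1 |
| 25% | 1.25 | 0.284 |
| 50% | 2.5 | 0.080 |
| 75% | 3.75 | 0.022 |
| 100% | 5 | 0.006 |

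With c held at 50%, the probability that none is counted is 0.606 at p = 1%, 0.366 at 2%, 0.080 at 5% and 0.006 at 10%.

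For the precision involved, exact 95% limits are 0 to 3.6% for 0/100 and 1.6 to 11.3% for 5/100. The SAP plans Clopper-Pearson limits for ADRs and SARs, not for this composite, so these show scale and are not output the SAP would produce.

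The counts are for the post-dosing part of these two components. The loss in subjects counted in the whole composite cannot be larger, since a subject with another composite event is counted anyway.

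**The case against.** The strongest reply is that nothing is missing. Protocol 12.1 counts any unfavourable and unintended sign as an AE, and section 12.4 makes the investigator responsible for recording all AEs observed. Appendix A, Group D, includes blood-pressure-decrease terms, so the protocol foresees such readings being reported as events. Appendix B can be read as the test that the committee applies to reported AEs rather than as a rule for finding cases. The charter may contain a vital-signs trigger. The readings are in any case listed by subject, and the trial is descriptive, so no test or comparison changes.

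Most of this stands, and it rules out three stronger readings that a reader might infer.

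- That qualifying readings never reach the endpoint. They do if the investigator records them, and the charter, which is not available here, may bring in others.
- That the composite is biased downward. Under-counting is possible but not shown: full reporting loses nothing.
- That two whole components out of eight are affected. Only their post-dosing part is. After release from the visit, a health care contact or a change of therapy is required as well.

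What remains is that the protocol and SAP contain no rule that ensures capture of events which the protocol itself defines by measurement. A listing without a flag does not supply one.

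**Conclusion.** The point holds as a gap in specification. For the period just after dosing, the definition rests on readings, the endpoint rests on reported and adjudicated AEs, and neither document connects the two. Capture depends on open-label investigator reporting or on the unseen charter, so under-counting is possible and, on the process described, any error is in that direction.

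The size is unknown. On the assumed 5% rate in 100 subjects, the expected count runs from 0 if none are reported to 5 if all are. The conclusion that capture is not ensured does not depend on those rates, but it does assume that the charter has no trigger of its own. If it has one, a sentence in the SAP citing it closes the capture question.

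This concerns a secondary safety endpoint in a trial with no hypothesis test. It is worth correcting because the data are already collected and the limits already written.

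**What to change.** In SAP 7.3.1 and 7.3.3:

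1. Flag by program each 5-15 and 20-40 minute post-infusion reading that meets the existing Appendix B item 7 or 8 limits relative to the pre-infusion value. Appendix B does not name the reference value, so the SAP should; it already computes change from pre-infusion.
2. State whether the reading taken during the infusion counts, since Appendix B refers to the period following administration.
3. Report n (%) of subjects with a flagged reading beside the adjudicated composite, overall and by lead-in trial.
4. Reconcile flagged readings against reported AEs before database lock, and refer unreported cases to the existing committee as far as the charter allows.
5. Show a composite that includes these cases as a supplementary display. The main composite should keep adverse events as its unit, since adding unreported readings to it would change the endpoint.

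No new data and no new threshold are needed. The cost is SAP wording, one derived flag and one pre-lock query, possibly a few more cases for the committee, and a slightly higher count where it is displayed. If the charter does not permit referral of readings that are not AEs, step 4 would need a charter change, and steps 1 to 3 and 5 can proceed without it, with step 5 then based on flagged rather than adjudicated cases and labelled so.

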7.4 Analysis and Presentation of the Secondary Efficacy Endpoints

The secondary efficacy endpoints are the following:

- Change in Hb from baseline to week 2 and months 3 and 6
- Change in s-ferritin, transferrin saturation (TSAT), and s-iron from baseline to week 2 and months 3 and 6

Change in Hb from baseline to week 2 and months 3 and 6 will be summarised by week using descriptive statistics overall and by lead-in trial for the ITT, and for the FAS and PP analysis sets, if applicable. Furthermore, change from baseline for the lead-in trial to current baseline, week 2 and months 3 and 6 including absolute Hb values will be summarised. Change in Hb concentrations over time will be presented using mean plots overall and by lead-in trial. Serum (s)-ferritin, TSAT and s-iron will be presented in similar ways using the ITT analysis set, only.

The efficacy data will be listed by lead-in-trial, subject and time point.

7.5 Handling of Missing Values

No imputation of missing values will be applied.

7.6 Multiplicity adjustments

In this one-armed extension trial, no formal statistical analyses will be performed and there will be no adjustment for multiplicity.

7.7 Sub-group and Centre Effects

Summary tables of demographics, efficacy and secondary safety endpoints will be prepared overall and by lead-in trial.

No effect of centres will be evaluated.

7.8 Interim Analysis

No interim analysis is planned.

8 Deviations from Protocol

The below describes the deviation in statistical methods as compared to the protocol text.

- In the protocol section 15.3 it is stated that the ITT analysis set will include all subjects. This has been changed to: The ITT analysis set will include all subjects, with the exception of screening failures.

- In the protocol section 15.5 it is stated that summaries will be prepared with respect to two baselines: Baseline in lead-in trial, and baseline in this extension trial. This will only be applied to the efficacy endpoints.
- In the protocol section 15.6 it is stated that the incidence of treatment-emergent ADRs and SARs will be presented, including two-sided 95 % CI. Instead a two-sided CI around the number of subjects with ADRs and SARs, respectively will be constructed.
- In the protocol section 15.6 it is stated that number of subjects who experience an ADR including SUSARs will be compared between treatment groups. This is not applicable in this one-armed trial.

9 Software

All statistical calculations described in this SAP will be done by [REDACTED] using SAS, release 9.4 or later (SAS Institute, Cary, NC, USA).

10 Reference List

Not applicable.
